## 2.0 STUDY OBJECTIVES

### 2.1 Primary Objective

- 2.1.1 Phase I: Characterize the safety and tolerability of intrapleural injection of talimogene laherparepvec alone and in combination with IV nivolumab
- 2.1.2 Phase II: Resolution ( $\leq 50$ cc drainage over three consecutive every other day drainages) of pleural fluid accumulation accompanied by patient-defined improvement in symptoms (dyspnea, cough and/or chest pain)..

### 2.2 Secondary Objectives

- 2.2.1 Estimate progression free survival (PFS) following nivolumab and talimogene laherparepvec per irRECIST.
- 2.2.2 Estimate overall survival (OS).
- 2.2.3 Estimate rates of response (RR) via irRECIST.
- 2.2.4 Further characterize the toxicity profile of intrapleural talimogene laherparepvec administered alone and in combination with IV nivolumab (Phase II).
- 2.2.5 Describe modified Borg Scale of Perceived Dyspnea over the course of therapy (Provided in 11.6 **Appendix F: Borg Scale**).

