### 2.4.2 Secondary Endpoints

**2.4.2.1 Median PFS.** PFS will be defined as the time from D1 of treatment until death or progression.

**2.4.2.2 Median OS.** OS is defined as the time from D1 of treatment to death from any cause.

**2.4.2.3 Tumor response** will be defined as the proportion of patients with reduction in tumor (irCR+irPR) per irRECIST criteria outlined in section 6.8.

**2.4.2.4 Clinician assessed toxicity** will be classified and graded according to the National Cancer Institute's Common Terminology Criteria for Adverse Events (NCI-CTCAE, version 5.0).

**2.4.2.5 Use of modified Borg rating scale** for perceived dyspnea (10 point scale from 1 to 10 which measures perception of dyspnea) [59, 60] (Provided in 11.6 **Appendix F: Borg Scale**).

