In Dose Level 2 (expected Phase II dose), the first 3 patients will receive both IP talimogene laherparepvec and IV nivolumab. The first dose of talimogene laherparepvec will be administered on Cycle 1, Day 1 at 4mL of  $10^6$  pfu/mL in 200 cc normal saline (IP) to seroconvert HSV-seronegative patients. Three weeks will be given for seroconversion. Subsequent doses of talimogene laherparepvec at 4ml of  $10^8$  pfu/mL + Nivolumab 240 mg IV will be administered every two weeks starting on Cycle 2, Day 1 for up to 8 cycles of therapy. Patients will be assessed for DLTs related to IP administration of talimogene laherparepvec after seroconversion and 2 cycles of combination therapy (i.e., 7 weeks of study treatment). If  $\geq 2$  patients experience DLT, the study will be discontinued. If 1 patient out of 3 has DLT, 3 additional patients will be recruited and treated at the same dose level. If 0 out of 3 or  $\leq 1$  patient out of 6 has a DLT in the dose level 2 cohort, the study will recruit additional patients in Phase II at this dose level and accrue a total of 24 patients as per study goal. All patients treated at dose level 2 in Phase I or Phase II, will be included in analyses of safety and efficacy. Safety stopping rules will ensure the safety of subjects receiving combination treatment in Phase II (see [Statistical Considerations in section 9.0.](#))

Subjects may continue talimogene laherparepvec for up to 9 cycles (i.e. alone or with nivolumab) until resolution of pleural effusion or they experience systemic disease progression. Subjects who have resolution of pleural effusion as defined by

the primary endpoints may continue nivolumab monotherapy per standard of care until disease progression (see section 4.2 for details on treatment and section 6.5.2).

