## 6.0 Evaluations and Assessments

### 6.1 Safety Run-in Cohort 1 (Talimogene Laherparepvec Only)

Assessments	Pre-Study 	Treatment Period  Cycle 1 is 3 weeks in length, subsequent cycles are Q2W							Follow up	
		Cycle 1 Day 1 	Cycle 1 Day 8	Cycle 2 Day 1	Cycle 2 Day 8	Cycle 3 Day 1	Cycle 4 Day 1	Cycle 5 - 9 Day 1	End of TXT 	Long Term FU 
Informed Consent	X									
HSV-1 antibody	X									
History 	X	X	X	X	X	X	X	X	X	X
Physical exam 	X	X	X	X	X	X	X	X	X	
Performance Status	X	X	X	X	X	X	X	X	X	
EKG	X						X			
Troponin	X						X			
Chest X-ray	X	As needed and/or after three consecutive drainages with $\leq 50$ cc drainage (every other day drainages) of pleural fluid drainage accompanied by patient-defined improvement in symptoms (cough, chest pain and/or dyspnea).							X	
Tumor measurement 	X							X 	X 	X
Pregnancy test 	X									
Hematology 	X 	X	X	X	X	X	X	X	X	
Serum chemistries 	X	X	X	X	X	X	X	X	X	
Liver function tests 	X	X	X	X	X	X	X	X	X	
Coagulation 	X									
Toxicity Assessment	X	X	X	X	X	X	X	X	X	X
Concomitant Meds	X	X	X	X	X	X	X	X	X	
talimogene laherparepvec IP Q3W 10  PFU		X								
talimogene laherparepvec IP Q2W 10  PFU				X		X	X	X		

Assessments	Pre-Study 	Treatment Period  Cycle 1 is 3 weeks in length, subsequent cycles are Q2W							Follow up	
		Cycle 1 Day 1 	Cycle 1 Day 8	Cycle 2 Day 1	Cycle 2 Day 8	Cycle 3 Day 1	Cycle 4 Day 1	Cycle 5 - 9 Day 1	End of TXT 	Long Term FU 
Patient Diary 		X	X	X	X	X	X	X	X	
Blood / urine / pleura samples to assess viral shedding		X 	X 	X 	X 	X 	X 		X 	
Blood sample for correlative studies 		X		X			X		X	
Tumor biopsy	X 									
Collection of pleural drainage 		X		X					X	
Buccal Swab	X 	X 								
Modified Borg 		X		X			X		X	
Survival analysis										X

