## Key to Time and Events Table Footnotes

1. Radiological assessments, EKG and physical exam may be performed up to 4 weeks prior to day 1 of treatment. Other evaluations except for pregnancy must be performed within 2 weeks prior to Cycle 1 Day 1 of treatment. Serum B-HCG must be performed within 72 hours prior to first dose of study medication for women of child-bearing potential. Screening labs performed within 72 hours prior to Cycle 1 Day 1 do not need to be repeated on C1D1.
2. The first treatment cycle with talimogene laherparepvec is 3 weeks in length (21 days) to allow for seroconversion (See Schema in 4.1). Subsequent treatment cycles are to be repeated every 2 weeks (14 days) X 8 cycles or until progression, whichever occurs first. **A window of +/- 2 days applies to all study visits within the treatment period.**
3. **Visit may be deemed optional at the behest of the investigator.**
4. The end of treatment/safety follow up visit should only occur when patients permanently stop study treatment and should be performed 30 days (+/-7 days) after the last dose of study medication. Patients who have an ongoing  $\geq$ grade 2 or serious AE (SAE) at this visit will continue to be followed until the event is resolved or deemed irreversible by the investigator. Patients stopping nivolumab should be monitored for at least 100 days after discontinuing the drug for the emergence of SAEs. After two years of follow-up per standard of care (**Q3 months +/- 15 days**) as outlined in the time and events table, subsequent follow up will be by phone contact or via medical records to document disease progression and survival information until death (Q3 months +/- 15 days).
5. Complete history at baseline only (to include smoking history); thereafter focused history on symptoms/toxicity physical exam to include height (baseline only), examination of the skin, weight, pulse oximetry, and vital signs.
6. Tumor imaging should remain consistent throughout study, and should include those thought by investigator to best capture status of disease. Examples include PET, contrasted computed tomography (CT) of the chest, abdomen and pelvis, and bone scan. During the treatment period scans should occur prior to Cycle 5 Day 1 and every 4 cycles after that until progression. Imaging following completion of study procedures should be per standard of care for the relevant disease state.

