### 6.3 Pre-Study Assessments for Safety Run in Cohorts and Phase II (Tables 6.1 and 6.2)

Screening evaluations are to be conducted within 2 weeks prior to start of protocol therapy. Scans for tumor evaluation must be done within 4 weeks prior to the start of therapy. (**Note:** Hematology and other lab parameters that are  $\leq$  grade 2 BUT still meet criteria for study entry are allowed. Furthermore, changes in laboratory parameters during the study should not be considered adverse events unless they meet criteria for dose modification(s) of study medication outlined by the protocol and/or worsen from baseline during therapy). Pre-study assessments include:

Complete medical history (including smoking history) and physical examination (including skin exam, height, and weight)

ECOG Performance Status (see appendix A)

Laboratory evaluations:

- CBC with differential
- Serum chemistries (potassium, sodium, calcium, creatinine, chloride, glucose, magnesium, phosphorus, BUN, albumin, uric acid, and total protein)
- Liver function tests (total bilirubin, direct bilirubin if indicated, alkaline phosphatase, AST, ALT)
- Troponin
- Serum pregnancy test in women of childbearing potential (Note: pregnancy test to be done within 72 hours of day 1 of treatment)
- Coagulation (PT/INR)
- HSV-1 antibody test
- Blood samples collected for correlative studies

EKG

Chest x-ray after thoracentesis (baseline)

Concomitant medication(s): All concomitant medications will be recorded.

Tumor evaluation: CT or MRI scan of the neck, results from physical examination head and neck, and chest imaging (x-ray or CT scan at discretion of physician)

Tumor biopsy: All subjects will have catheter placed per standard of care, therefore fresh biopsy should be easily accessible. If fresh biopsy is unavailable, archival will be accepted.

Toxicity evaluation: Use NCI CTCAEv5.0 for notation of any baseline toxicity  
Modified Borg Scale of Perceived Dyspnea (Provided in 11.6 Appendix F: Borg Scale): Scale ranging from 0 (no dyspnea) to 10, which evaluates perceived level of shortness of breath.

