## 11.6 Appendix F: Borg Scale

### \*Instruction for Borg Dyspnea Scale

Use this scale to rate the difficulty of your breathing.

It starts at number 0 where your breathing is causing no difficulty at all and progresses through to number 10 where your breathing difficulty is maximal.

How much difficulty is your breathing causing you right now?

0	Nothing at all
0.5	Very, very slight (just noticeable)
1	Very slight
2	Slight
3	Moderate
4	Somewhat severe
5	Severe
6	
7	Very severe
8	
9	Very, very severe (almost maximal)
10	Maximal

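### The modified Borg dyspnea scale is not scheduled between Cycle 4 Day 1 (day 50) and the end-of-treatment visit, so the objective of describing it over therapy is met on treatment only through day 50

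*Combined protocol and SAP*

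**What the plan says.** Objective 2.2.5 reads "Describe modified Borg Scale of Perceived Dyspnea over the course of therapy". Both time-and-events tables (6.1 for the virus-only cohort, 6.2 for the combination cohort and expansion) mark the scale at C1D1, C2D1, C4D1 and end of treatment. Neither marks it at C3D1 or in the column for Cycle 5 onward. The visit text agrees: 6.4.1, 6.4.3, 6.4.5 and 6.5.1 list the Borg, while 6.4.4 (Cycle 3) and 6.4.6 (Cycle 5 onward) do not. Section 6.3 also lists it before the study, but neither table marks it in the pre-study column.

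The table footnotes say that "The end of treatment/safety follow up visit should only occur when patients permanently stop study treatment", timed 30 ± 7 days after the last study medication. Virus dosing ends at Cycle 9 at the latest. Under 4.1.1, combination patients whose effusion has resolved "may continue nivolumab monotherapy per standard of care until disease progression".

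On the range, 2.4.2.5 describes a "10 point scale from 1 to 10 which measures perception of dyspnea". Section 6.3 has "Scale ranging from 0 (no dyspnea) to 10, which evaluates perceived level of shortness of breath". The Appendix F instruction says "It starts at number 0 where your breathing is causing no difficulty at all and progresses through to number 10", and its response list includes 0.5.

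Section 8.3 does not name the Borg. It says only that available quality-of-life data will be summarized.

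**The concern.** An objective about the course of therapy needs readings spread over therapy. Here the on-treatment readings stop at the fourth of nine possible dosing visits. Virus may be given through Cycle 9 unless the effusion resolves or systemic disease progresses, so an effusion can resolve after day 50, when no dyspnea score is due until treatment has ended. That last score is taken about a month after the final dose, so it describes the patient off treatment.

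At stake is whether the trial can report how breathlessness changed during Cycles 5 to 9. Readings not taken at those visits cannot be recovered later. Patients attend them anyway for examination, laboratory tests, toxicity review and the drainage diary.

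**Working it through.** **Inputs.** Cycle 1 lasts 21 days and later cycles 14 days (Tables 6.1 and 6.2, footnote 2). There are at most nine virus doses (Table 6.2, footnote 9). The end-of-treatment visit is 30 ± 7 days after the last study medication (Table 6.1, footnote 3; Table 6.2, footnote 4).

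**Check on a stated figure.** Section 4.1.4 gives three cycles as 7 weeks: 21 + 14 + 14 = 49 days = 7 weeks. This reproduces, and puts C4D1 on day 50.

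**Visit days.** C1D1 = 1; C2D1 = 1 + 21 = 22; each later Day 1 adds 14. So C3 = 36, C4 = 50, C5 = 64, C6 = 78, C7 = 92, C8 = 106 and C9 = 120. On-treatment Borg readings fall on days 1, 22 and 50. The five dosing visits on days 64, 78, 92, 106 and 120 have none.

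**Gap after C4D1.** End-of-treatment day = last dose day + 30; gap = that day − 50.

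| Last study dose | Day | End of treatment (± 7) | Gap from C4D1 (± 7) |
|---|---|---|---|
| C4 | 50 | 80 | 30 |
| C5 | 64 | 94 | 44 |
| C6 | 78 | 108 | 58 |
| C9 | 120 | 150 | 100 |
| C13, nivolumab only | 176 | 206 | 156 |
| C17, nivolumab only | 232 | 262 | 212 |
| C21, nivolumab only | 288 | 318 | 268 |

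The last three rows are assumed durations, because the protocol gives no expected time on nivolumab. They apply only if continued nivolumab counts as study medication. The ± 7 days is the end-of-treatment window; the ± 2 days allowed for treatment visits is ignored.

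**Share of the dosing period.** For nine cycles, (120 − 50) / (120 − 1) = 70/119 = 59% of the time from first to last virus dose follows the last on-treatment score.

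**Effect of adding C5 to C9.** The longest interval between on-treatment scores through day 120 becomes 50 − 22 = 28 days (C2D1 to C4D1). For a patient whose last dose is C9, the interval to end of treatment becomes 30 days (23 to 37).

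**The case against.** The strongest reply is that this is a descriptive secondary objective with no test attached, and that the schedule gives three on-treatment scores, an end-of-treatment score and, under 6.3, a pre-study score. Nine cycles is a maximum, since virus dosing stops at resolution; a patient who stops after C5 has a gap of 44 days. All of this stands. It limits the point without removing it, because the protocol allows treatment through Cycle 9 and beyond, and nothing is recorded on treatment after day 50.

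Several stronger readings are tempting, but the documents do not support them:

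- *For responders the final score always follows progression.* Nivolumab after resolution is optional. Section 4.1 also lets it end for toxicity or withdrawal, and the virus-only cohort gets none on study. The protocol calls it standard care after resolution, yet 4.2 lists nivolumab among the study treatments, and no passage says whether it counts for timing the visit. The delay from last dose to visit is the same for every patient, whatever the outcome.
- *The Borg underpins the primary endpoint.* Sections 2.1.2 and 2.4.1.2 ask for improvement in symptoms as judged by the patient. They neither name the Borg nor set a threshold on it.
- *The C1D1 score is taken after instillation and so biases change toward improvement.* Section 6.4.1 does list the Borg below dosing, but list order is not a timing rule: the same section lists post-dose samples above dosing. Section 6.3 also lists a pre-study score. What is missing is a stated timing and a stated baseline.
- *Scores of 0 and 0.5 will be lost.* Section 2.4.2.5 itself points to Appendix F, and every visit section that lists the Borg uses 0 to 10. No form restricted to 1 to 10 is described.
- *Many patients will die before a later reading.* The four-month median survival in 1.2 describes malignant effusion in general, not this selected population.
- *C3D1 is needed as well.* No defect is shown in the 28 days between C2D1 and C4D1.

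**Conclusion.** The schedule meets objective 2.2.5 on treatment only through day 50. For a full nine-cycle course the unmeasured interval is about 100 days (93 to 107), and 59% of the time from first to last virus dose follows the last on-treatment score. These figures assume dosing on schedule with the last study medication on C9D1. The gap is shorter if treatment stops early. It is longer if continued nivolumab counts as study medication, and the final score may then mix the effect of treatment with that of progression.

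It would go too far to say that the Borg cannot describe dyspnea at all: the first seven weeks and one post-treatment value are covered. The primary endpoint, alpha, power and sample size are unaffected. The range in 2.4.2.5 is a text error with no demonstrated effect on the data. The case for change is that a clear gap in a stated objective can be closed very cheaply.

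**What to change.** - Add the modified Borg to the existing C5 to C9 Day 1 visits in Tables 6.1 and 6.2 and in 6.4.6.
- State that it is taken before that visit's instillation at every dosing visit, including C1D1.
- In 8.3, name the Borg summary: on-treatment change from the pre-instillation baseline through C9, with the end-of-treatment value reported separately.
- Reconcile the pre-study Borg in 6.3 with the tables, so that it is clear which score is the baseline.
- State whether nivolumab continued after resolution counts as study medication when timing the end-of-treatment visit, so that the final score can be interpreted.
- Correct 2.4.2.5 to 0 to 10 including 0.5, as in Appendix F (text only).

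The cost is about a minute per visit for one question at visits already scheduled, slightly more data entry, and edits to the tables and text.

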### 2.3 Exploratory Objectives

**Via multi-parametric flow cytometry and mRNA-sequencing methods:**

- 2.3.1 Explore tumor molecular subtype and immune gene expression signatures
- 2.3.2 Explore comprehensive T-cell quantification and phenotyping, including the change in effector lymphocytic infiltrates, regulatory T cell populations, and clonal expansion of tumor-infiltrating T cells

- 2.3.3 Explore if it is possible to predict signature response vs. resistance expression from key clinical, tumor, and immune features.
- 2.3.4 Measure expression of PD-1, PD-L1, PD-L2, and other immune check point molecules

## 2.4 Study Endpoints

### 2.4.1 Primary Endpoint

**2.4.1.1 Phase I:** Clinician assessed toxicity will be classified and graded according to the National Cancer Institute's Common Terminology Criteria for Adverse Events (NCI-CTCAE, version 5.0).

**2.4.1.2 Phase II: Resolution ( $\leq 50$ cc drainage over three consecutive every other day drainages) of pleural fluid accumulation accompanied by patient-defined improvement in symptoms (dyspnea, cough and/or chest pain).**

### 2.4.2 Secondary Endpoints

**2.4.2.1 Median PFS.** PFS will be defined as the time from D1 of treatment until death or progression.

**2.4.2.2 Median OS.** OS is defined as the time from D1 of treatment to death from any cause.

**2.4.2.3 Tumor response** will be defined as the proportion of patients with reduction in tumor (irCR+irPR) per irRECIST criteria outlined in section 6.8.

**2.4.2.4 Clinician assessed toxicity** will be classified and graded according to the National Cancer Institute's Common Terminology Criteria for Adverse Events (NCI-CTCAE, version 5.0).

**2.4.2.5 Use of modified Borg rating scale** for perceived dyspnea (10 point scale from 1 to 10 which measures perception of dyspnea) [59, 60] (Provided in 11.6 **Appendix F: Borg Scale**).

## 3.0 PATIENT ELIGIBILITY

### 3.1 Inclusion Criteria

Patients must meet all of the following inclusion criteria to participate in this study:

- 3.1.1 Signed a written IRB-approved informed consent and HIPAA authorization for the trial.
- 3.1.2 Be  $\geq 18$  years of age on day of signing informed consent.

- 3.1.3 ECOG Performance Status  $\leq 2$ . (See Appendix A: ECOG Performance Status).
- 3.1.4 Histologically or cytologically confirmed stage IV metastatic cancer.
- 3.1.5 Confirmation of malignant pleural effusion via imaging (CXR, CT scan, ultrasound, MRI, or PET/CT) and cytology for which pleurX catheter placement is standard of care.
- Dose Level 1: Either no systemic therapy available per standard of care, or delay in administration of systemic therapy considered clinically acceptable.
  - Dose Level 2/Phase II: Nivolumab alone would be an acceptable standard treatment OR have a tumor type with prior data for PD1 efficacy OR non-pleural disease is not considered a significant risk to the patient OR refractory to standard therapies.
- 3.1.6 Demonstrate adequate organ function as defined in the table below. All screening labs should be performed within 14 days of treatment initiation.

System	Laboratory Value 
Hematological	
Absolute neutrophil count (ANC)	$\geq 1000 /\mu\text{L}$
Platelets	$\geq 50,000 / \mu\text{L}$
Hemoglobin	$\geq 10 \text{ g/dL}$ (acceptable to reach this through transfusion)
Renal	
Calculated creatinine clearance (Cockcroft-Gault) 	$\geq 45 \text{ mL/min}$
Coagulation	
INR or PT	$\leq 1.5 \times \text{ULN}$ unless the subject is receiving anticoagulant therapy, in which case PT and PTT/aPTT must be within therapeutic range of intended use of anticoagulants
Hepatic	
Serum total bilirubin	$\leq 1.5 \times \text{ULN}$ OR Direct bilirubin $\leq \text{ULN}$ for subjects with total bilirubin levels $> 1.5 \text{ ULN}$
AST (SGOT) and ALT (SGPT)	$\leq 2.5 \times \text{ULN}$ OR $\leq 5 \times \text{ULN}$ for subjects with liver metastases
Albumin	$> 2.5 \text{ mg/dL}$
Pulmonary	
Pulse Oximetry	At least 90% on room air ( OR 95% on oxygen)
Cardiac	
EKG	No clinically relevant cardiac dysfunction
Troponin	$< 0.3$

System	Laboratory Value 
--------	-------------------------------

[figure not shown]
1. See [Appendix B](#) (Section 11.2) for Cockcroft-Gault formula.
  2. Hematology and other lab parameters that are  $\leq$  grade 2 BUT still meet criteria for study entry are allowed. Furthermore, changes in laboratory parameters during the study should not be considered adverse events unless they meet criteria for dose modification(s) of study medication outlined by the protocol and/or worsen from baseline during therapy.
- 3.1.7 Recovered from all reversible toxicities related to their previous treatment (other than alopecia) to  $\leq$  grade 1 or baseline; exceptions to this criterion may be allowed following review by the principal investigator for toxicities that are not expected to be exacerbated by nivolumab or talimogene laherparepvec. Grade 2 peripheral neuropathy will not result in exclusion as neither study agent would be expected to exacerbate it.
- 3.1.8 No history of untreated brain metastasis. Treated brain metastases must not be known to be progressive, symptomatic, or currently requiring  $> 10$  mg of prednisone or prednisone equivalents within two weeks prior to study drug administration.
- 3.1.9 Females of childbearing potential must have a negative serum pregnancy test within 72 hours prior to receiving the first dose of study medication. Females of childbearing potential must agree to use 2 methods of effective contraception or abstain from heterosexual sex throughout the treatment period and for 5 months after the last dose of study treatment. Females of childbearing potential are women who have not been surgically sterilized (have undergone a hysterectomy, bilateral tubal ligation, or bilateral oophorectomy) or have not been free of menses for  $>1$  year.
- 3.1.10 Male patients with female partners must have had a prior vasectomy or agree to use an adequate method of contraception (i.e. double barrier method: condom plus spermicidal agent) starting with the first dose of study therapy through 7 months after the last dose of study treatment.
- 3.1.11 As determined by the enrolling physician or protocol designee, ability or willingness of the patient to understand and comply with study procedures.
- 3.2 Exclusion Criteria**
- Patients meeting any of the following exclusion criteria will not be able to participate in this study:
- 3.2.1 Receiving any investigational agent, or using an investigational device, currently or within 28 days or 5 half-lives of Day 1 of treatment on this study, whichever is longer.

- 3.2.2 Has had prior chemotherapy, targeted small molecule therapy, or radiation therapy within 2 weeks prior to study Day 1.
- 3.2.3 Has had a prior monoclonal antibody within 4 weeks prior to study Day 1, or who has not recovered to,  $\leq$  Grade 1 toxicity at baselines from adverse events due to agents administered more than 4 weeks earlier. Exceptions to these criteria may be allowed at the discretion of the investigator for toxicities that are not expected to be exacerbated by nivolumab or talimogene laherparepvec (e.g., alopecia, peripheral neuropathy, etc).
- 3.2.4 Any concurrent chemotherapy, IP, biologic or hormonal therapy for cancer treatment. Concurrent use of hormonal therapy for non-cancer-related conditions (e.g., hormone replacement therapy) is acceptable.
- 3.2.5 Major surgery within 28 days prior to day 1 of study treatment from which the patient has not completely recovered.
- 3.2.6 Has a diagnosis of immunodeficiency or is receiving systemic steroid therapy or any other form of immunosuppressive therapy within 7 days prior to the first dose of trial treatment.
- 3.2.7 Has a known secondary malignancy that is progressing or requires active treatment. Exceptions include basal cell carcinoma of the skin, squamous cell carcinoma of the skin, or in situ cervical cancer that has undergone potentially curative therapy.
- 3.2.8 Has an active automimmune disease requiring systemic treatment within the past 3 months or a documented history of clinically severe autoimmune disease, or a syndrome that requires systemic steroids or immunosuppressive agents; subjects with resolved childhood asthma/atopy would be an exception to this rule. Subjects that require intermittent use of bronchodilators or local steroid injections would not be excluded from the study. Subjects with hypothyroidism stable on hormone replacement or Sjorgen's syndrome will not be excluded from the study. Replacement therapy (e.g., thyroxine, insulin, or physiologic corticosteroid replacement therapy for adrenal or pituitary insufficiency, etc.) is not considered a form of systemic treatment. Subjects with vitiligo, Grave's disease, or psoriasis not requiring systemic treatment (within the past 2 years) are not excluded.
- 3.2.9 Has a history of non-infectious pneumonitis that required steroids; currently active non-infectious pneumonitis; or evidence of interstitial lung disease.
- 3.2.10 Has an active infection requiring systemic therapy or history of uncontrolled infection.
- 3.2.11 Has a history or current evidence of any condition, therapy, or laboratory abnormality that might confound the results of the trial, interfere with the subject's participation for the full duration of the trial, or is not in the best interest of the subject to participate, in the opinion of the treating investigator. This includes

- known psychiatric or substance abuse disorders that would interfere with cooperation with the requirements of the trial. This also includes unstable angina, serious uncontrolled cardiac arrhythmia, uncontrolled infection, or myocardial infarction  $\leq$  6 months prior to study entry.
- 3.2.12 Has inadequate home environment or social support to safely complete the trial procedures.
  - 3.2.13 Is pregnant or breastfeeding.
  - 3.2.14 Known human immunodeficiency virus (HIV), hepatitis C virus (HCV) or evidence of active hepatitis B virus (HBV).
  - 3.2.15 Has a multi-loculated pleural effusion that would not lead to relief of dyspnea from drainage of a single loculation.
  - 3.2.16 Current active hepatic or biliary disease (with exception of patients with Gilbert's syndrome, asymptomatic gallstones, or stable chronic liver disease per investigator assessment).
  - 3.2.17 Active herpetic skin lesions or prior complications of herpetic infection or requires intermittent or chronic systemic (intravenous or oral) treatment with an antiherpetic drug (e.g., acyclovir), other than intermittent topical use.

